IRB Study Number: 20171006

Version #, Date:

Title: Prospective Comparative Study of Non-ablative Laser with and without Lytera™ 2.0 Pigment Correcting Serum on the Appearance of Skin Tone and Photoaging

NCT: NCT03661697

Last IRB Modification and Approval: 3/25/2019

1) **Protocol Title**

Effect of Combination Laser Treatment and Skin Brightening Topical on the Appearance of Skin tone and Photoaging: A Pilot Study

2) **Objectives***

Our objective is to **determine** the effects of (1) basic skin care regimen + “active” (Lytera 2.0) vs (2) basic skin care regimen only, both groups combined with laser treatment on the **appearance** of skin tone and photoaging on the face

Our hypothesis is that combination laser + brightening cream (active arm) will **improve appearance** of skin tone and photoaging of the face when compared to combination laser + non-brightening cream.

3) **Background***

Photodamaged skin can be characterized by alterations to skin tone, fine wrinkles, and tactile roughness. These changes in skin appearance are usually due to chronic exposure to ultraviolet radiation. It is a common and often distressing skin condition that can also be difficult to treat. A wide variety of treatments are available to treat these alterations in skin such as cosmetic topicals, chemical peels, dermabrasion, cosmetic lasers, neuromodulators, and dermal fillers. Topicals are often the starting point for treatment of photodamage and can be used before, during, and after office procedures to augment outcomes for patients. Laser treatment is indicated for correction of existing mild-severe photodamage/aging skin. After treatment, patients can expect to have more uniform skin tone, improved texture, more radiant skin, minimized pore size appearance, and skin that looks and feels clear and brilliant. Results can be immediate but are also progressive, improving over multiple treatments. Clinicians have now begun to investigate the usefulness of integrating skincare products and cosmetic lasers.

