The gold standard for improving the appearance of photoaging and hyperpigmentation (specifically solar lentigines) has been a hydroquinone-containing product. Makino et al compared Lytera 2.0 (a Correcting Serum) to Hydroquinone 4% in a randomized, split-face double blind study in subjects with moderate to severe skin tone. Lytera 2.0 showed statistically significant results at 2 weeks and Hydroquinone 4% showed statistically significant results at 4 weeks. Lytera 2.0 is a cosmetic product that is for brightening the appearance of skin does not contain any hydroquinone or other ingredient classified as a drug. (Please see the Lytera 2.0 patient brochure in the attached documents).The 1927 nm fractional non-ablative

laser has also been found to be effective in treating the pigment in photo-damaged skin.

In our study, only patients with Fitzpatrick skin types I through IV will be recruited as those with a higher level than skin type IV can be prone to overproduction of melanin following certain laser types. Fitzpatrick skin type I is highly sensitive, always burns, and never tans. Type II is very sun sensitive, burns easily, and hardly tans. Type III is sensitive, sometimes burns, and tans to light brown. Type IV is minimally sun sensitive, burns minimally, and tans to moderate brown. Type V is insensitive skin, rarely burns, and tans well. Type VI is insensitive, never burns, and is deeply pigmented.

Although laser treatment and lightening skin care products have been shown to improve skin tone and photo aging, currently, there is no clinical data to support the efficacy and longevity of combination laser treatment + brightening skin care products for photoaging and skin tone. Our study will attempt to observe if combination non-ablative laser (1927 nm also known as Clear and Brilliant) and Lytera 2.0 Correcting Serum will improve the appearance of skin tone and photoaging when compared to laser alone.

4) Inclusion and Exclusion Criteria*

Inclusion criteria:

- Healthy adult male and female patients 18 years and older
- Fitzpatrick skin types I-IV
- Has at least mild mottled skin tone of the face (score of 2 or more on a 5 point skin tone scale)
- Has at least 2 areas of the face with significant roughness, dyspigmentation, or fine lines or has all these characteristics in 1 or more areas

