- Willing to refrain from using any other topical products on the face, systemic retinoids, or steroids, facial peels or other facial laser procedures throughout the duration of the study
- Willing to refrain from any cosmetic procedure including but not limited to facial surgery, dermal fillers, and neuromodulators for the duration of the study
- Willing to use only the facial skin care product regimen provided for the study
- Willing to avoid extended periods of sun exposure and the use of tanning beds during the study
- Willing to have photographs taken of the face to be used de-identified in evaluations, publications, and presentations
- For females: proof that they are not pregnant (urine pregnancy test)
- English-speaker

Exclusion criteria:

- Has any uncontrolled systemic disease (such as autoimmune disorders and

connective tissue disorders such as lupus erythematosus or Sjogren's syndrome
Has any active infection in face
Has history of any skin conditions that could interfere with treatment
Has used self-tanner recently
Is currently participating in another drug research study
Is NOT willing to refrain from using any other topical products such as skin lightening, retinoids, alpha/beta-hydroxyl acids, salicylic acid, vitamins C or D, steroids, or antibiotics on the face or systemic retinoids, steroids, facial peels, neuromodulators, dermal fillers, facial surgery, or other facial laser procedures throughout the duration of the study
For females: is pregnant
Non English-speaker

Individuals will be screened for eligibility via questionnaires that address each of the inclusion and exclusion criteria. Our final study sample will include the subjects who met the inclusion/exclusion criteria and did not voluntarily drop out of the study or develop adverse effects that prohibited them from safely completing the study. We will exclude adults unable to consent, patients under the age of 18, pregnant women, and prisoners.

5) Number of Subjects*

After recruiting our subjects, 14 patients will be randomized into either arm of the study (7 in each arm).

6) Study-Wide Recruitment Methods*

This is a single center study. We will recruit subjects from a clinical database of the practice of [name]. We will use several recruitment methods including invitation via a scripted email providing information describing the study protocol and end-points, scripted invitation telephone calls, and flyers.

7) **Study Timelines***

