One month prior to laser treatments (washout period), 14 male and female subjects with moderate hyper pigmentation and photo damage of the face will be randomized to 2 skincare regimens.

The regimens are:

- "Placebo arm" – Basic skin care regimen* (Facial Cleanser, TNS ceramide Treatment Cream (standard post-procedure moisturizer), and Essential Defense Mineral Shield Broad Spectrum SPF35 (all-physical sunscreen))
- "Lytera arm" – Basic skin care regimen + **Lytera 2.0**, which will be added between the Facial Cleanser and TNS Ceramide Treatment Cream

*The basic skin care regimen is a standard regimen used in several skincare product experiments

After cleansing the face, the patients in the Lytera arm will apply one pump of the pigment-correcting serum in a circular motion to the entire face

including the forehead, cheeks, chin, nose, and neck with care to avoid the eyes. The Lytera 2.0 is applied prior to applying moisturizer and sunscreen.

On laser treatment days, patients will come into the office without having applied any topical cream that day. Lidocaine topical may or may not be applied over the face avoiding the eyes (lidocaine use will be at discretion of Principal Investigator), and patients will be given protective goggles to shield the eyes during laser treatment. Next, the laser wand is pressed to the face and passed over the skin in various horizontal and vertical directions. Treatment takes 20 to 30 minutes.

Standardized digital photographs will be taken at baseline and at each subsequent visit using the Canfield VISIA Complexion Analysis (VISIA-CA) camera system at the highest resolution in a consistent position. Pictures will be taken before laser treatments on Visit 2 and Visit 3.

The subjects will complete an exit questionnaire after completion of the study at their last study visit (Visit 4). Through the questionnaire, we will obtain information on subject satisfaction with the study as well as their opinion of how their skin has changed. We hope to use the responses to assess efficacy of our skincare regimen and to improve future related research protocols.

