Local tolerability including itching, redness, burning, or pain will be assessed at each visit by the investigator. Subjects will also be asked to assess discomfort during treatment and also to maintain diary at home to record any side effects after each facial laser treatment. To lessen the probability of risks of laser treatment, will use the standard pulse energy and coverage known to produce the minimal amount of side effects, increase subject comfort, and allow for rapid healing.

Once all subjects have completed the study, one independent evaluator will retrospectively analyze the VISIA high definition photography data that was taken at each visit. The independent observer will evaluate the photos of each patient for clinical efficacy and tolerability using two validated grading scales (Modified Pigmentation Area and Severity Index (MoPASI) and Global Aesthetic Improvement Scale (GAIS)) at baseline and at weeks 5, 8, and 12.

The GAIS is used to evaluate change in aesthetics after intervention. 0 = worse, 1 = no change, 2 = improved, 3 = much improved, 4 = very much improved. The MoPASI is a dermatologist-developed modified scale derived from the validated Melasma area and severity index scale. Pigmentation is assessed in 4 sections of the facial skin, and three variables are assessed within each region: percentage of area involved, darkness of pigment in the area, and pattern of involvement in the area. Subjects will complete self-

assessment questionnaires at baseline and at the end of the study.

The Clear and Brilliant 1927nm laser has been used extensively in facial cosmetic surgery for skin resurfacing to improve the skin changes associated with photoaging and skin tone. The laser is FDA approved for this use (see Device attachments for documentation). The Solta Medical Company has proven that it produces safe and effective treatment and even in combination with topicals, has a high safety profile (see supporting documents).

Lytera 2.0 Correcting Serum, a Skin Medica product, is a non-hydroquinone, non-drug advanced Correcting Serum that has been proven to minimize the appearance of skin discoloration and dark spots. Our proposed study is to observe the effect of Lytera 2.0 on skin tone, and will not evaluate any underlying changes to skin structure or function. The assessments in the proposed study are observational and do not include biopsy or other method.

Key ingredients of Lytera 2.0 Pigment Correcting Serum:

Tranexamic Acid

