Phenylethyl Resorcinol

Niacinamide and Tetrapeptide 30

Marinen Extract blend

Phytic Acid

Other ingredients: Vitis Vinifera SCE, Plankton Extracts, Hydroxyacetophenone, Artemisia Capillaris, Marine Exopolysaccharides

Data that will be collected about subjects (see attached data collection form):

Age

Gender

Race

Past medical history including current and past illnesses, current medications, allergies, past surgeries, any past adverse effects to facial cosmetics, family history, social history including alcohol, tobacco, or illicit drug use.

Past skin care history including any surgical cosmetic procedures, fillers, injectables, lasers, or topical treatments.

Fitzpatrick skin type (I-IV)

Evaluation of baseline skin tone

Adverse effects experienced throughout the study

MoPASI scores

GAIS scores

Representative photographs of subjects at baseline and at subsequent visits

10) **Data and Specimen Banking***

Data will be stored on Box, a secure file sharing, storage, and collaboration system using a password-protected, encrypted laptop. Data will be stored for 1 year after the completion of the study. Only [name], principal investigator and [name] and [name], co-investigators and study coordinator will have access to the data. Data will only be released by Drs. [name] or [name] for publication of study results.

Stored data will include:

Age

Gender

Race

Past medical history including current and past illnesses, current medications, allergies, past surgeries, any past adverse effects to facial cosmetics, family history, social history including alcohol, tobacco, or illicit drug use.

Past skin care history including any surgical cosmetic procedures, fillers, injectables, lasers, or topical treatments.

Fitzpatrick skin type (I-IV)

Evaluation of baseline skin tone

Adverse effects experienced throughout the study

MoPASI scores

GAIS scores

Representative photographs of subjects at baseline and at subsequent visits

11) **Data Management***

Statistical analysis will be conducted to determine the effect size necessary to power a study. All statistical tests will be two-sided and interpreted at a 5% significance level. The primary analyses will be based on the MoPASI and GAIS scores. Scores after each laser treatment will be compared to baseline scores using the appropriate statistical test.

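### The only efficacy contrast the analysis plan names is post-laser score versus baseline; the Lytera versus basic-regimen comparison that the hypothesis needs is not specified

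*Combined protocol and SAP*

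**What the plan says.** The question is comparative throughout. Section 2 sets the two regimens against each other, "both groups combined with laser treatment", and hypothesises improvement "of skin tone and photoaging of the face when compared to combination laser + non-brightening cream". Section 3 repeats the aim: the combination "will improve the appearance of skin tone and photoaging when compared to laser alone". Section 5 states that "14 patients will be randomized into either arm of the study (7 in each arm"), and Section 9 shows that the regimens differ only by Lytera 2.0.

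The statistical plan is four sentences in Section 11. They give the purpose (an effect size with which to power a study), the test level (two-sided 5%), the scores on which the primary analyses rest (MoPASI and GAIS), and one contrast: "Scores after each laser treatment will be compared to baseline scores using the appropriate statistical test". None of the four mentions arm, group, Lytera or a treatment difference.

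Two details in Section 9 bear on how that contrast would work. On timing: "Pictures will be taken before laser treatments on Visit 2 and Visit 3". On the second score: "The GAIS is used to evaluate change in aesthetics after intervention. 0 = worse, 1 = no change". Yet both scales are to be graded from the photographs, including the "Global Aesthetic Improvement Scale (GAIS)) at baseline and at weeks 5, 8, and 12".

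**The concern.** Both arms receive the laser and the basic regimen, and Section 15 tells patients to expect more even skin tone after two laser treatments. Scores may therefore improve from baseline in both arms whether or not the serum does anything. A change from baseline that is not compared between the randomised arms cannot separate the serum from what the arms share.

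Two things are at stake. The first is the conclusion: a significant pre/post change in the Lytera arm could be reported as support for Lytera. The second is the pilot's stated statistical purpose. A later trial of Lytera would be sized on the between-arm difference and its variability. A pre/post effect size that includes the laser response could mis-size that trial, and Section 11 does not say which of the two it means.

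**Working it through.** **1. Is an arm comparison specified anywhere?** Every other mention of analysis or efficacy review was checked.

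- Section 8 (Study Endpoints) defines only when a patient finishes.
- Section 9 says that questionnaire answers will help assess efficacy and that one evaluator will grade the photographs.
- Section 12 says that safety and efficacy data are reviewed after each visit.
- Section 17 says that results are shared once analysed.
- Section 19 says that a biostatistician will help with the analysis.

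None names a comparison between arms.

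**2. What does the named contrast contain?** Photographs at Visits 2 and 3 precede that day's laser. The scores after each laser treatment are therefore those at Visit 3 (after one session) and Visit 4 (after both). Relative to Visit 1, the components are:

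| Change from Visit 1 | Laser | Basic regimen | Time | Serum |
|---|---|---|---|---|
| Lytera arm | yes | yes | yes | yes |
| Basic-regimen arm | yes | yes | yes | no |
| Difference between arms | cancels | cancels | cancels | remains |

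The cancellation holds in expectation, through randomisation. Only the last row answers the hypothesis, and it is the row that is not written down.

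**3. GAIS.** The scale rates change, with 1 meaning none. A baseline rating has nothing to rate. Comparing follow-up GAIS with baseline at best tests whether the follow-up rating differs from 1.

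**4. Illustration of the pre/post contrast with zero serum effect.** The documents give no SD and no laser effect, so the shared change d is assumed, in SDs of the change. For a paired t-test at two-sided 5%, the noncentrality is d√n and the power P(n) comes from the noncentral t with n − 1 degrees of freedom. For n = 7 and d = 1.0, the noncentrality is √7 = 2.65 against a critical value of 2.45. If each arm is tested separately, the chance that only the Lytera arm is significant is P(7) × (1 − P(7)).

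| Assumed d | One arm, n = 7 | Pooled, n = 14 | Only Lytera arm significant |
|---|---|---|---|
| 0.5 | 0.20 | 0.41 | 0.16 |
| 0.8 | 0.43 | 0.79 | 0.24 |
| 1.0 | 0.60 | 0.93 | 0.24 |
| 1.5 | 0.91 | >0.99 | 0.08 |

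Section 11 does not say whether arms are tested separately or pooled, so both are shown. These are powers to detect a real pre/post change. They say nothing about Lytera.

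**5. What the between-arm comparison can deliver at 7 v 7.** The plan gives no power or effect size behind the 14, so there is no planned figure to reproduce. In SDs of the outcome, which is a different unit from step 4:

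- Unadjusted 95% CI half-width = t(0.975, 12) × √(2/7) = 2.179 × 0.5345 = 1.16 SD.
- Unadjusted 80% power is reached at 1.63 SD. Power at 0.5, 0.8, 1.0 and 1.5 SD is 0.14, 0.28, 0.41 and 0.73.
- With ANCOVA at assumed baseline correlations of 0.3, 0.5 and 0.7, simulation with chance baseline imbalance gives a mean CI half-width of 1.15, 1.04 and 0.86 SD, and 80% power at 1.64, 1.49 and 1.23 SD.

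**The case against.** The strongest reply is that the arm comparison is implied. The sentence naming the primary analyses gives no contrast, and the next sentence does not call itself the primary analysis. In a protocol with a comparative objective and randomised arms, change from baseline compared by arm is a natural reading. This stands in part. A reader might infer that the primary analysis is fixed as within-arm and so cannot test the hypothesis; the text does not support that, because it leaves the contrast open. But an implied comparison still leaves visit, test, baseline adjustment and estimate to be chosen after the scores are seen.

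The second reply is that this is a pilot with 7 per arm, where a between-arm test would rarely be decisive, and that the comparison can be computed later from data already planned. That is true, and it limits the harm to lost pre-specification and a risk of misreporting. It does not remove the gap: Section 11 still sets a 5% test level, and the effect size it promises has to come from some contrast.

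Third, the pre/post rates depend on assumed effects. That also stands, and the point does not rest on them.

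**Conclusion.** The point holds as a gap in specification. The design asks a between-arm question; the only contrast written down is change from baseline, and taken literally it cannot isolate Lytera or yield the between-arm effect size. This follows from the text alone and needs no assumption.

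The numerical size is illustrative. With no serum effect, a single arm of 7 would show a significant pre/post change in 20% to 91% of trials if the shared change were 0.5 to 1.5 SD of the change, a range chosen here because the documents give no figure.

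It would go too far to say that an arm comparison is excluded, or that GAIS should lose its place among the primary scores. The plan supports neither. The gap should be closed before the scores are analysed, because it decides what the trial can conclude.

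**What to change.** Replace the contrast sentence in Section 11 with text such as:

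> The primary analyses compare the randomised arms (Lytera minus basic regimen) at Visit 4: MoPASI by ANCOVA adjusted for Visit 1 MoPASI, with a 95% CI and a rank-based or permutation check; GAIS by an exact Wilcoxon rank-sum test with an effect estimate and 95% CI. Within-arm changes from baseline are descriptive and will not be used to conclude that Lytera adds benefit. The effect size for a future study is the between-arm difference with its CI.

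ANCOVA, the rank-sum test and Visit 4 (the only visit after both laser sessions) are proposals. Any other between-arm test and visit named in advance would also close the gap. GAIS remains a primary score, as the plan states. Whether two primary scores need a multiplicity rule is a separate decision.

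The cost is a few sentences, with no new visits or measurements. The drawback is imprecision: at low baseline correlation, adjustment gains almost nothing over the unadjusted ±1.16 SD. The report should lead with the estimate and its interval, and a non-significant result should not be read as evidence of no effect.

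### Section 11 names no between-arm contrast and no baseline covariate for MoPASI, so with 7 per arm a chance imbalance can shift this trial's estimate of the serum effect

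*Combined protocol and SAP*

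**What the plan says.** The analysis plan is a few sentences in Section 11 (Data Management). The tests are fixed as follows: "All statistical tests will be two-sided and interpreted at a 5% significance level". The outcomes are named: "The primary analyses will be based on the MoPASI and GAIS scores". Baseline enters once: "Scores after each laser treatment will be compared to baseline scores using the appropriate statistical test". The section gives its purpose as finding the effect size on which a study could be powered. It names no test, model, covariate or comparison between arms.

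The hypothesis in Section 2 is between arms: laser plus serum should improve the appearance "of skin tone and photoaging of the face when compared to combination laser + non-brightening cream". Section 5 states that "14 patients will be randomized into either arm of the study (7 in each arm". No stratification or other balancing is described.

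Section 4 admits anyone with a "score of 2 or more on a 5 point skin tone scale" and Fitzpatrick types I to IV. Section 9 has the photographs graded on MoPASI and GAIS "at baseline and at weeks 5, 8, and 12", and the Section 7 schedule lists MoPASI at all four visits. A MoPASI score from before the regimens start is therefore already collected. On the other outcome, Section 9 says "The GAIS is used to evaluate change in aesthetics after intervention".

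**The concern.** The quantity that a later study would be sized on is the difference between the Lytera arm and the basic-regimen arm. Section 11 does not define it, so whoever analyses the data must choose how baseline enters. The two simplest choices err in opposite directions when the arms start unequal. Suppose the Lytera arm happens to start with more pigment. A comparison of raw follow-up scores then makes the serum look worse, because part of the starting difference persists. A comparison of changes makes it look better, because the arm that starts higher tends to fall further. With the test left open, the direction of the error would depend on a choice made after the data are seen.

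At 7 per arm a sizeable starting difference is not rare, and the measurement that would remove its effect is already in the data.

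**Working it through.** **Inputs from the documents.** 7 per arm (Section 5); two-sided 5% level (Section 11); MoPASI at Visit 1 and three later visits (Sections 7 and 9). No effect size, SD or power is given, so the sample size of 14 can be neither reproduced nor refuted. For orientation, 7 per arm gives 80% power for a difference of 1.63 SD (t-test, 12 df).

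**Assumptions.** The correlation ρ between baseline and follow-up MoPASI is not in the documents and is taken from 0.3 to 0.9. Scores are taken as normal with equal SD at both times, with a common slope in the two arms and a higher score meaning more pigment.

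**Step 1: chance of imbalance.** The SE of the baseline difference is √(2/7) = 0.535 SD.
- P(|difference| > 0.5 SD) = 2 × [1 − Φ(0.5/0.535)] = 35%.
- P(|difference| > 0.75 SD) = 16%, and P(|difference| > 1 SD) = 6%.

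**Step 2: shift for a given imbalance d.** With no serum effect, the expected arm difference is +ρd on raw scores, −(1 − ρ)d on change scores, and 0 from a model with baseline as covariate. For d = 0.5 SD and ρ = 0.5 this gives +0.25, −0.25 and 0 SD.

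**Step 3: average shift in imbalanced trials.** When one arm starts higher by more than 0.5 SD, the mean imbalance is 0.79 SD. At ρ = 0.3 the formulas give 0.3 × 0.79 = +0.24 and −0.7 × 0.79 = −0.55. Simulation of 7 v 7 (60,000 to 100,000 trials per ρ) agrees to about 0.01 SD:

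| ρ (assumed) | Shift, raw (SD) | Shift, change (SD) | Shift, adjusted (SD) | Mean 95% CI width, change (SD) | Mean 95% CI width, adjusted (SD) |
|---|---|---|---|---|---|
| 0.3 | +0.23 | −0.56 | within 0.005 | 2.69 | 2.29 |
| 0.5 | +0.40 | −0.39 | within 0.005 | 2.28 | 2.09 |
| 0.7 | +0.55 | −0.24 | within 0.005 | 1.76 | 1.72 |
| 0.8 | +0.63 (0.8 × 0.79) | −0.16 | 0 (formula) | 1.44 | 1.44 |
| 0.9 | +0.71 | −0.08 | within 0.005 | 1.02 | 1.05 |

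**Step 4: precision.** Relative to 2·SD²/7, the variance of the arm difference is 1 for raw scores, 2(1 − ρ) for change scores, and (1 − ρ²)(1 + 1/(14 − 4)) = 1.1(1 − ρ²) with the covariate.
- Adjustment beats raw scores only if ρ > √(1 − 1/1.1) = 0.30.
- It beats change scores only if ρ < 2/1.1 − 1 = 0.82.
- From the table, the adjusted interval against the change score is about 15% narrower at ρ = 0.3, 8% at 0.5 and 2 to 3% at 0.7, equal at 0.8 and about 3% wider at 0.9.
- Against raw scores at ρ = 0.3 there is no gain (about 2.28 v 2.30 SD).
- Power for a 1 SD effect, change score against adjusted, is 41% v 47% at ρ = 0.5 and 60% v 63% at 0.7, with no gain at 0.8.

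**Step 5: error rates.** At ρ = 0.5 the unadjusted tests reject about 8% of the time in the 35% of trials with imbalance above 0.5 SD, and about 3.3% in the rest: 0.35 × 8.2 + 0.65 × 3.3 ≈ 5%. The adjusted test is at about 5% in the imbalanced trials too. Averaged over all trials, all three estimators have mean zero under no effect.

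**The case against.** A reader might infer that the plan ignores baseline altogether. It does not: the Section 11 sentence compares later scores with baseline, which points to within-patient change. What is missing is a covariate, and the open wording on the test does not rule one out.

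A reader might also infer that an unadjusted analysis is biased or inflates the type I error. Randomisation prevents that on average. The 8% figure applies only to imbalanced trials at one assumed correlation.

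The strongest objection is that Section 11 defines no serum estimate that could be shifted. The larger gap is the missing comparison between arms, and whoever writes that comparison would settle the adjustment in the same sentence. This stands, and is why the two belong in one correction. It does not dispose of the point, because adding an arm contrast on change scores alone would leave the shift in place.

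Two smaller points also stand. Section 9 describes the subjects as having moderate hyperpigmentation, which suggests a narrower spread than the entry criterion allows, and no MoPASI SD is given. The 35% is in SD units and so does not depend on the spread, but the shift in MoPASI points does. Second, a linear model with a common slope is itself an assumption for a composite grading score in 14 subjects, or fewer, since Section 4 leaves dropouts out of the final sample.

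**Conclusion.** The point holds for MoPASI, as an inexpensive improvement to a pilot rather than a flaw that invalidates it. Section 11 leaves the arm comparison undefined and does not use the Visit 1 score as a covariate. There is about a one in three chance of a baseline imbalance large enough to move an unadjusted estimate materially. For change scores, the reading closest to Section 11, the average shift in such a trial is material at low to moderate correlation and small at 0.9. For raw scores the pattern is reversed. Removing the shift is the main benefit, and it holds at every correlation examined.

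A reader might conclude that precision is certainly being lost. The documents do not support this, because the gain depends on a correlation they do not give. Nor does the point extend to GAIS, which is itself a rating of change and has no starting level to adjust for.

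The sizes rest on the assumptions of normal scores, equal SD and a common slope, and on 7 analysed subjects per arm.

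**What to change.** Add to Section 11:

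> The serum effect on MoPASI is the Lytera minus basic-regimen difference at Visit 4 (week 12), from a linear model of the Visit 4 MoPASI score with arm and Visit 1 MoPASI as the only covariate, reported with a 95% confidence interval. Earlier visits are analysed in the same way as supportive. GAIS is compared between arms without this covariate.

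The visit must be named because there are three follow-up assessments. The covariate should be the Visit 1 score and not the Visit 2 score: Section 7 starts the regimens in the four weeks before Visit 2, so that score may already reflect the serum. With 14 subjects no further covariates should be added; Fitzpatrick type and age can be listed by arm.

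The cost is one sentence, no new data and one error degree of freedom (11 instead of 12). If the correlation is about 0.9, the interval is about 3% wider than with a change score.
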